### **Definition of Tumor Response Using irRC**

#### **Calculation of Immune-related Sum of Products of Diameters (irSPD)**

The irSPD incorporates measurable new lesions that may have developed on-study, providing an assessment that includes both index and new lesions. The tumor assessment performed during Screening will serve as the baseline for determination of tumor response using irRC.

irSPD at Baseline: The sum of the product of the diameters for all index lesions identified prior to randomization. At baseline, irSPD and SPD are the same.

irSPD at TA: For every post-randomization TA collected, per protocol Section 5.1 or as clinically indicated including post mWHO PD TA, the irSPD at TA will be calculated using tumor imaging scans. Both index lesions and any measurable new lesions that have developed on study will be included.

irSPD Nadir: For tumors that are assessed more than one time after baseline, the lowest value of the irSPD (irSPD Baseline or irSPD at TA) is used to classify subsequent TAs for each subject. Because ipilimumab treatment may result in complex tumor dynamics in which index lesions may shrink while new lesions appear, the irSPD nadir may be different from the SPD nadir, and may occur either before or after the SPD nadir.

At baseline, the irSPD is measured and recorded.

At each subsequent assessment timepoint, a separate assessment of timepoint overall response will be obtained for that timepoint. The sum of products of perpendicular diameters calculated and recorded at each post-baseline timepoint for immune-related response purposes (irSPD) include measurements of index lesions and also include measurable new lesions which are not too small to measure at this timepoint. A value of 25 mm^2 (5 mm x 5 mm) is imputed for each index and previously measurable new lesion which is present but too small to measure.

### Timepoint Overall Response Using irRC

- The overall assessment of immune-related response reported at each timepoint will be based on the following criteria:
- Immune-related CR (irCR): Complete disappearance of all tumor lesions (index and non-index together with no new measurable/unmeasurable lesions).
- Immune-related PR (irPR): A decrease, relative to baseline of the irSPD (as defined above) of 50% or greater is considered an irPR.
- Immune-related SD (irSD): irSD is defined as an evaluable response that fails to meet criteria for immune-related CR or immune-related PR, in the absence of irPD.
- Immune-related Progressive Disease (irPD): At least a 25% increase in the irSPD (based on irSPD of all index lesions and any measurable new lesions, as defined above) over the nadir irSPD, or the occurrence of any new measurable lesions if the SPD nadir is “0” (including when no measurable lesions are present at baseline).
- Immune-related Unknown Response (irUN): Tumor assessments which cannot be evaluated (e.g., due to image quality, inability to assess all relevant lesions, etc.) will be reported as irUN.

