#### Inclusion criteria:

- Histological/cytological diagnosis of melanoma.
- AJCC Stage IV (any T, any N, M1), metastatic, progressive, refractory, melanoma.
- Patients may have advanced unresectable Stage IV disease, resectable Stage IV disease, or recently resected Stage IV disease (<10 weeks prior) with no apparent disease (NAD)
- Eastern Cooperative Oncology Group (ECOG) Performance Status  $\leq 1$  (see **Appendix B**).
- Serum albumin  $\geq 3.0$  gm/dL.
- Adequate organ function including:
  - Marrow: Hemoglobin  $\geq 10.0$  gm/dL, absolute granulocyte count (AGC)  $\geq 1,000/\text{mm}^3$ , platelets  $\geq 75,000/\text{mm}^3$ , absolute lymphocyte count  $\geq 475/\text{mm}^3$ .
  - Hepatic: Serum total bilirubin  $\leq 2.5$  x upper limit of normal (ULN), ALT (SGPT) and AST (SGOT)  $\leq 2.5$  x ULN.
  - Renal: Serum creatinine (sCr)  $\leq 1.5$  x ULN.
- Prior therapy for melanoma that may include surgery, radiation therapy, immunotherapy including interleukins and interferon, and/or  $\leq 2$  different regimens of systemic chemotherapy, targeted therapy, or other experimental systemic therapies. Prior treatment with immune checkpoint inhibitors is not allowed (see Exclusion criteria).
- Patients must be  $\geq 4$  weeks since major surgery, radiotherapy, chemotherapy (6 weeks if they were treated with nitrosureas) or biotherapy/targeted therapies.
- Patients must have the ability to understand the study, its risks, side effects, potential benefits and be able to give written informed consent to participate. Patients may not be consented by a durable power of attorney (DPA).
- Male and female subjects of child producing potential must agree to use *contraception or avoidance of pregnancy measures* while enrolled on study and receiving the experimental drug, and for one month after the last immunization.

Exclusion criteria:

- Age <18-years-old.
- *Active* CNS metastases or carcinomatous meningitis. Patients with CNS lesions that have been treated and who have no evidence of progression in the brain on CT/MRI for  $\geq 1$  month are eligible.
- Pregnant or nursing women due to the unknown effects of immunization on the developing fetus or newborn infant.
- Other malignancy within five years, except that the following may be eligible:
  - patients curatively treated for localized squamous or basal cell carcinoma of the skin or for carcinoma *in situ* of the uterine cervix (CIN) or breast,

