#### **Disease Parameters**

Measurable disease: Measurable lesions are defined as those that can be accurately measured in at least one dimension (longest diameter to be recorded) as  $\geq 20$  mm by chest x-ray or as  $\geq 10$  mm with CT scan, MRI, or calipers by clinical exam. All tumor measurements must be recorded in millimeters (or decimal fractions of centimeters).

Malignant lymph nodes: To be considered pathologically enlarged and measurable, a lymph node must be  $\geq 15$  mm in short axis when assessed by CT scan (CT scan slice thickness recommended to be no greater than 5 mm). At baseline and in follow-up, only the short axis will be measured and followed.

Non-measurable disease: All other lesions (or sites of disease), including small lesions (longest diameter  $< 10$  mm or pathological lymph nodes with  $\geq 10$  to  $< 15$  mm short axis), are considered non-measurable disease. Bone lesions, leptomeningeal disease, ascites, pleural/pericardial effusions, lymphangitis cutis/pulmonitis, inflammatory breast disease, and abdominal masses (not followed by CT or MRI), are considered as non-measurable.

Note: Cystic lesions that meet the criteria for radiographically defined simple cysts should not be considered as malignant lesions (neither measurable nor non-measurable) since they are, by definition, simple cysts.

‘Cystic lesions’ thought to represent cystic metastases can be considered as measurable lesions, if they meet the definition of measurability described above. However, if non-cystic lesions are present in the same patient, these are preferred for selection as target lesions.

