## ***12.2 Blinding and Randomization***

This is an open-label, randomized study. Patients will be randomized to receive immune checkpoint therapy plus dorgenmeltucel-L or immune checkpoint therapy alone in a 1:1 ratio. Patients enrolled in this and later protocol amendments will be stratified by treatment choice and disease status and categorized as follows:

- 1) Patients with unresectable advanced disease
- 2) Patients with resectable advanced disease who receive the immunotherapy in advance of resection
- 3) Patients with resected isolated advanced disease who are treated in a no apparent disease (NAD) state

With sufficient sample size enrolled per disease status category, the randomization process is designed to provide balance between the two treatment arms within each of the disease status categories. The number of patients in each stratum will not be restricted.

Patients enrolled in Protocol Version 1 were not stratified; however the disease status criteria of these patients will be collected to properly account for the randomization strata in the statistical analysis. Further details regarding the randomization procedure are available in the Randomization Plan.

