### **Efficacy Analyses**

The primary efficacy endpoint is PFS, where disease progression is defined according to RECIST v1.1. Progression free survival will be summarized using the Kaplan-Meier method of estimation, including the 25th, 50th, and 75th percentiles of time to progression with 95% confidence intervals. Kaplan-Meier plots will be produced by disease status strata to examine the difference in response rates between treatment groups. A stratified log rank test will be applied to test for treatment effect on PFS.

Overall response rate is defined as subjects with a best overall response of at least stable disease. Subjects' best overall response, as determined by the investigator from RECIST, will be summarized by presenting the numbers and percentages of subjects in each response category. The overall response rate will be summarized similarly. Ninety-five percent confidence intervals (CIs) will be constructed for the overall response rate.

The duration of overall response is measured from the time measurement criteria are met for CR or PR (whichever is first recorded) according to RECIST v1.1 until the first date that recurrent or progressive disease is objectively documented (taking as reference for progressive disease the smallest measurements recorded since the treatment started). Duration of overall response will be analyzed in a similar manner to PFS.

Duration of stable disease is measured from the start of the treatment until the criteria for progression are met according to RECIST v1.1, taking as reference the smallest measurements recorded since the treatment started, including the baseline measurements. Duration of stable disease will be analyzed in a similar manner to PFS.

Overall survival is defined as the time to death or last contact and will be summarized in a similar manner to PFS.

As additional secondary endpoints, analysis of PFS, overall response rate, duration of overall response, and duration of stable disease will be repeated using the irRC criteria to identify disease response.

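### Under the irRC rules, a patient with no measurable baseline lesion who relapses only at non-measurable sites is scored irSD, so irPFS does not register the relapse

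*Combined protocol and SAP*

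**What the plan says.** Section 9.1, Timepoint Overall Response Using irRC, gives irPD two triggers. One is a rise of at least 25% in irSPD over its nadir. The other is "the occurrence of any new measurable lesions if the SPD nadir is" zero, and the text says that this covers patients with no measurable lesion at baseline. irCR requires that no lesion remains and that no new lesion, measurable or not, has appeared. irPR requires a fall of at least 50% from baseline irSPD. irUN is kept for assessments that cannot be evaluated. What is left is stable disease: "irSD is defined as an evaluable response that fails to meet criteria for immune-related CR or immune-related PR, in the absence of irPD".

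The irSPD calculation counts index lesions and measurable new lesions only. Disease Parameters classes "Bone lesions, leptomeningeal disease, ascites, pleural/pericardial effusions", among others, as non-measurable. Immune-related Endpoints adds that a new lesion by itself is not irPD.

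Section 3.1 admits recently resected patients with no apparent disease. Section 12.2 makes them a randomization stratum, "Patients with resected isolated advanced disease who are treated in a no apparent disease (NAD) state", and states: "The number of patients in each stratum will not be restricted".

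Section 12.3, Efficacy Analyses, repeats PFS, response rate, duration of response and duration of stable disease under irRC as additional secondary endpoints. It also says: "Overall response rate is defined as subjects with a best overall response of at least stable disease". Populations to be Analyzed makes all randomized subjects the primary efficacy population. Definitions in Section 9.1, by contrast, treats a patient as evaluable for objective response only if there was measurable disease at baseline.

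**The concern.** irPFS is meant to give a second view of progression that allows for the unusual tumor dynamics of immunotherapy. It can do so only if a clear relapse is able to become an event. Both irPD triggers depend on measurable disease, yet the trial sets no measurable-disease entry criterion and enrols a whole stratum with no disease to measure. In that stratum the event that matters is recurrence, and recurrence confined to bone, meninges or an effusion has no route to irPD.

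A second question concerns the irRC response rate. Stable disease counts as response, and the population for this rate is not settled. Patients with nothing to respond could therefore enter the numerator.

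**Working it through.** The plan gives no figure to reproduce on this point. The check applies the written rules to defined cases and then sets a range on the number of patients.

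**Case A: NAD at baseline, readable scan, new bone lesion only.** Baseline, nadir and current irSPD are all 0.

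| Category | Requirement | Met? |
|---|---|---|
| irPD, trigger 1 | irSPD up at least 25% over nadir | No, irSPD stays 0 |
| irPD, trigger 2 | nadir 0 and a new measurable lesion | No, the lesion is non-measurable |
| irCR | no new lesion of either kind | No |
| irPR | irSPD down at least 50% from baseline | No, nothing can fall from 0 |
| irUN | assessment cannot be evaluated | No, the scan is readable |
| irSD | none of the above | Yes |

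The RECIST table for patients with non-measurable disease scores any new lesion as PD, so the same scan is PD under RECIST and irSD under irRC. Two comparison cases behave as expected: an NAD patient with a new measurable lesion is irPD, and an NAD patient with no lesion is irCR.

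**Case B: only non-measurable disease at baseline, with a new effusion or unequivocal growth of existing disease.** The same steps give irSD. RECIST gives PD. Definitions in Section 9.1 says that patients with such disease are assessed on presence, absence or unequivocal progression of the lesions, and the irRC section has no category that uses the last of these. The passages conflict.

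**How long the relapse goes unregistered.** It becomes an irPFS event once a measurable new lesion is imaged. New Lesion Measurement requires scans after RECIST progression only until the sum has risen by 25% or study therapy stops. Section 4.4 takes patients whose tumor progresses off study, apart from an allowance for mild early progression. The follow-up calendar leaves imaging after progression to standard of care. A later measurable lesion may therefore never be recorded. Section 12.3 does not say whether death is an irPFS event.

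**Response denominator.** With all randomized subjects as the population and response defined as stable disease or better, NAD patients count as irRC responders. Under Definitions in Section 9.1 they are not evaluable for response. Section 12.3 does not say which applies.

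**Number affected (assumed ranges, because the documents give neither input).** Let N0 be the number of 100 patients with a baseline sum of 0, and q the share of them who relapse only at non-measurable sites. The number scored irSD instead of irPD is N0 × q.

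| N0 | q = 10% | q = 20% | q = 30% |
|---|---|---|---|
| 10 | 1 | 2 | 3 |
| 20 | 2 | 4 | 6 |
| 30 | 3 | 6 | 9 |

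**The case against.** The best defense is that irRC deliberately refuses to call progression on a new lesion alone, and the protocol says so. For a patient with measurable index lesions this stands. With a nadir of 0, however, the protocol already departs from that principle by letting a new measurable lesion count. It therefore recognises that these patients need their own rule, and that rule leaves out non-measurable relapse.

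A reader might infer that the relapse is counted as a response. The documents do not support this as a flat statement, because Definitions limits response evaluability to measurable baseline disease. What remains is a conflict over the denominator. Moreover, an NAD patient with one clean scan already has a best response of irCR. The relapse itself produces a best response of irSD only if it appears on the first post-baseline scan.

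A reader might also see a contradiction on a single scan: all index lesions vanish, a small new measurable lesion appears, and the result is both irPR and irPD. This rests on the irPD trigger naming the SPD nadir, whereas the irSPD section warns that "the irSPD nadir may be different from the SPD nadir". But that section uses the irSPD nadir to classify subsequent assessments. If the SPD nadir is read the same way, it comes from earlier scans, is above 0 on the scan in question, and does not fire the trigger.

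Finally, a reader might carry the gap over to the primary endpoint, because Evaluation of Non-Target Lesions refers new lesions to irRC before they count as progression. Section 12.3 defines primary PFS by RECIST v1.1, and the RECIST tables score a new lesion as PD. Those passages need reconciling, but they do not establish that primary PFS has the same defect.

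**Conclusion.** The point holds for NAD patients on the plain wording: a relapse confined to non-measurable sites is irSD, and irPFS misses it unless a measurable lesion is imaged later. For patients with only non-measurable disease at baseline, the irRC rules lack a route for unequivocal progression and contradict other parts of Section 9.1. The population for the irRC response rate is likewise contradictory.

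On the assumed ranges, about 1 to 9 of 100 patients would be affected. The range rests on the assumed share with a baseline sum of 0 and the assumed share of those who relapse only at non-measurable sites. The documents give no basis for a direction of bias between arms. The irRC endpoints are secondary, and Multiplicity Issues in Section 12.3 rules out formal tests of them. It would go too far to conclude that the irRC results cannot support the RECIST result at all. The defect is limited, but it is clear and cheap to correct.

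**What to change.** 1. In Timepoint Overall Response Using irRC, for patients with no measurable lesion at baseline, score as irPD any unequivocal new lesion, measurable or not, and any unequivocal progression of non-index disease. Use the confirmatory scan, at least 4 weeks later, that New Lesion Measurement already requires. State this as an exception to the rule in Immune-related Endpoints that a new lesion alone is not irPD.
2. In Section 12.3, compute the irRC response rate, duration of response and duration of stable disease only in patients with measurable disease at baseline, in line with Definitions in Section 9.1. Report NAD patients by recurrence, through irPFS, only.
3. Optionally, change the SPD nadir to the irSPD nadir in the irPD rule for consistency.

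The cost is protocol and SAP wording, with no added scans or visits. The downside is a smaller denominator for the irRC response rate and durations.

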#### 4.4 *Duration of Therapy*

Patients whose tumor progresses on therapy will be off-study. However, mild progression ( $\leq 25\%$  increase in tumor size) at the beginning of the treatment is allowed, given the usual delayed response / pseudoproggression seen with immunotherapy (Wolchok et al., 2009).

Patients who experience a SAE which triggers stopping rules for immune checkpoint inhibitors ipilimumab, nivolumab, or pembrolizumab as described in their respective package inserts will be permanently discontinued from the immune checkpoint inhibitor. They can be continued on dorgenmeltucel-L (if in Arm 1) once recovered from immune checkpoint inhibitor toxicity.

Patients are also off study who:

- experience intercurrent illness that prevents further administration of treatment;
- decide to withdraw from the study;
- experience general or specific changes in the patient's condition that render them unacceptable for further treatment in the judgment of the investigator.

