## **Response Criteria**

### **Evaluation of Target Lesions**

**Complete Response (CR):** Disappearance of all target lesions. Any pathological lymph nodes (whether target or non-target) must have reduction in short axis to <10 mm.

**Partial Response (PR):** At least a 30% decrease in the sum of the diameters of target lesions, taking as reference the baseline sum diameters.

**Progressive Disease (PD):** At least a 20% increase in the sum of the diameters of target lesions, taking as reference the smallest sum on study (this includes the baseline sum if that is the smallest on study). In addition to the relative increase of 20%, the sum must also demonstrate an absolute increase of at least 5 mm. (Note: the appearance of one or more new lesions is also considered progressions).

**Stable Disease (SD):** Neither sufficient shrinkage to qualify for PR nor sufficient increase to qualify for PD, taking as reference the smallest sum diameters while on study.

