### New Lesion Measurement

The irRC are tumor assessment criteria that have been developed to better capture the activity of immunotherapeutic agents. These criteria have been used with success in clinical studies that were performed with ipilimumab in advanced metastatic melanoma and in lung cancer.

Additional tumor response data will be collected, beyond what is required to apply the RECIST criteria. More specifically, the investigator will have to record in the CRF the bi-dimensional measurements for each new lesion which has become measurable in each tumor assessment.

To support evaluation of progression-free survival based on irRC criteria (irPFS) in this indication, investigators must perform tumor assessments (including new lesion measurements) during the Toxicity/Progression Follow-up Phase in subjects who have experienced RECIST progression until the total sum of product diameters (SPD including new lesions) has increased 25% or more from the nadir or until subjects discontinue study therapy regardless of whether the subject is initiating subsequent therapy. All available post RECIST progression tumor imaging- based assessments during this phase in the study must be entered into the CRF, including any standard of care assessments and any assessments performed while under non-study subsequent cancer therapy.

Any subject who develops an objective tumor response (CR or PR) or progression (PD) is required to undergo confirmatory scans no less than 4 weeks since the prior scan in order to verify the reliability of the radiologic finding. Sites are encouraged to collect additional CT scans after RECIST PD has been confirmed, as long as a subsequent line of therapy has not been initiated.

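### The irPD definition is met at a single scan, and nothing makes the required confirmatory scan decide irPD or the irPFS date

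*Combined protocol and SAP*

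**What the plan says.** All of the tumour-assessment rules are in Section 9.1.

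- **RECIST PD** (Evaluation of Target Lesions): "At least a 20% increase in the sum of the diameters of target lesions" over the smallest sum on study, and "the sum must also demonstrate an absolute increase of at least 5 mm". New lesions are also PD. The non-target subsection adds unequivocal non-target progression.
- **irSPD** is an area measure. Its baseline is "The sum of the product of the diameters for all index lesions identified prior to randomization".
- **irPD** (Timepoint Overall Response Using irRC): "At least a 25% increase in the irSPD (based on irSPD of all index lesions and any measurable new lesions, as defined above"). The rise is measured from the nadir. There is no absolute minimum and no mention of a second scan. If the nadir is zero, any new measurable lesion is irPD.
- **Confirmation** (New Lesion Measurement): a subject with CR, PR or PD "is required to undergo confirmatory scans no less than 4 weeks since the prior scan". The Immune-related Endpoints subsection also asks for confirmatory scans beyond RECIST PD to support irPFS.
- **How long irPFS assessment is mandatory** (New Lesion Measurement): after RECIST progression, "until the total sum of product diameters (SPD including new lesions) has increased 25% or more from the nadir", or until study therapy ends.
- **25% allowances**: Section 4.4 tolerates mild early progression of up to 25% in tumour size, "given the usual delayed response / pseudoproggression seen with immunotherapy". The non-target subsection refers suspected progression below 25%, or new lesions, to irRC. Neither says whether the 25% is in diameters or products.

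Section 12.3 bases primary PFS on RECIST v1.1 and repeats PFS, response and the two duration endpoints under irRC as additional secondary endpoints. Secondary efficacy endpoints are not formally tested.

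**The concern.** The irRC endpoints are there to separate true progression from the delayed or paradoxical changes expected with immunotherapy. A second scan makes that separation for lesions that first enlarge and then settle. The plan asks for the scan but does not use it in the endpoint.

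From the same images, one analyst could date irPFS at the first 25% crossing, another could require confirmation, and a third could reverse an unconfirmed crossing. All three would be following the document. In addition, 25% on an area scale is a small change in diameter, so ordinary measurement error can cross it. A difference between RECIST PFS and irPFS could then reflect the scale and the noise rather than pseudoprogression.

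**Working it through.** The plan gives no diameter equivalent for its irRC threshold, so there is no stated figure to reproduce.

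**1. Uniform growth (same proportion on both axes and in all lesions).**
- irPD in diameter terms: √1.25 − 1 = 0.118, or +11.8%.
- RECIST PD in area terms: 1.20² − 1 = 0.44, or +44%.
- One 20 mm lesion: irPD at 20 × 0.118 = +2.4 mm; RECIST PD at max(20% × 20, 5) = +5.0 mm.
- A 30 mm sum: irPD at 30 × 0.118 = +3.5 mm; RECIST PD at +6.0 mm.

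**2. Short axis growing at a fraction k of the long-axis rate g.** Solve (1 + g)(1 + kg) = 1.25.

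| k | long-diameter growth at irPD |
|---|---|
| 1 | 11.8% |
| 0.5 | 15.8% |
| 0.25 | 19.3% |
| 0 | 25.0% |

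The two relative thresholds meet at g = 20% when k = (1.25/1.20 − 1)/0.20 ≈ 0.21. Below that, the RECIST 20% is reached first, provided the 5 mm minimum is also met.

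**3. Two lesions, only the one of size a growing (both axes), the other of size b stable.** irPD needs √(a² + 0.25(a² + b²)) − a. RECIST needs max(0.20(a + b), 5).
- a = 20, b = 20: irPD at √600 − 20 = +4.5 mm; RECIST at +8.0 mm. irPD comes first.
- a = 10, b = 50: irPD at √750 − 10 = +17.4 mm; RECIST at +12.0 mm. RECIST comes first.

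**4. The 25% allowances, for uniform growth.** If 25% means diameters, RECIST PD between +20% and +25% is already +44% to +56% in products (1.25² − 1 = 0.5625), hence already irPD. If it means products, growth under 25% is under 11.8% in diameter and is not RECIST PD. Either way, referral to irRC defers no RECIST PD that arises from uniform target-lesion growth. It can still defer PD based on new lesions.

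**5. Measurement noise with no true change.** Everything here is assumed, because the documents give no measurement error: circular lesions of 12 to 40 mm, independent relative error on each diameter, a baseline and four later scans, and the nadir updated at each scan. Confirmed irPD means that an independent repeat scan also exceeds 1.25 times the same nadir.

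| SD per diameter | lesions | irPD, first crossing | RECIST PD | irPD, confirmed |
|---|---|---|---|---|
| 7% | 1 | 33% | 13–14% | 12% |
| 7% | 2 | 14% | 5% | 3% |
| 7% | 3 | 6% | 1% | 1% |
| 7% | 5 | 1% | <0.1% | 0.1% |
| 5% | 1 | 10% | 2% | 2% |
| 10% | 1 | 60% | 35% | 31% |

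**6. The link between scan and endpoint.** The irPD definition does not mention the confirmatory scan. The confirmation sentence names PD, and the next sentence speaks of RECIST PD; neither names irPD. Section 12.3 gives no event or date rule for irPFS. The Section 8 follow-up note leaves imaging after progression to standard of care, so a rise that is irPD but not RECIST PD may or may not lead to a confirmatory scan.

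**The case against.** The best defence is that confirmation is already in the plan. A subject who progresses is "required to undergo confirmatory scans no less than 4 weeks since the prior scan in order to verify the reliability" of the finding, and a per-scan category would not normally carry a confirmation clause, since confirmation works across scans. This stands to the extent that a reader who infers that irRC has no confirmation at all would be wrong. It does not supply the missing rule: whether an unconfirmed crossing is an event, and on what date. Likewise, the 25% clause on mandatory assessment sets how long scanning must continue. It does not cancel the confirmation requirement, although it ends the mandatory irPFS assessments at a first crossing.

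A reader might also infer that irPFS always calls progression earlier than RECIST, or that irRC is more lenient only for new lesions. The documents support neither. RECIST comes first in the uneven-growth cases in steps 2 and 3. New lesions alone are not irPD unless the nadir is zero, and non-target progression that counts under RECIST does not enter irPD.

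Finally, the noise figures depend on an assumed SD and are largest with one lesion. Up to five target lesions are allowed, and with five the false-irPD rate at 7% SD is about 1%. That is a fair limit on the size of the problem.

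**Conclusion.** The point holds as a gap in the endpoint definition. irPD is met at one scan, and the scan meant to verify progression has no stated role in irPD or in the irPFS date. For uniform growth the threshold is 11.8% in diameter with no minimum size, so growth of existing target lesions will often be irPD before RECIST PD. That ordering depends on growth shape and lesion mix.

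The noise risk matters mainly for patients with one or two lesions: about 33% and 14% false irPD at 7% SD, falling to 12% and 3% with confirmation. With one lesion, confirmation takes it from 10% to 2% at 5% SD and from 60% to 31% at 10% SD. These are illustrations under no true change and independent errors, not forecasts of event rates.

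It would be tempting to extend this to the trial's main result. The documents do not support that: primary PFS is defined by RECIST v1.1, the sample size does not use irPD, and the irRC endpoints are secondary and untested. The change is worth making, but it is not critical.

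**What to change.** For the irRC secondary endpoints:

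1. Define the irPD event as a rise of at least 25% over nadir irSPD that is still met at the scan at least 4 weeks later, dated at the first scan.
2. State that PD in the confirmation sentence includes irPD.
3. State how a missing confirmatory scan is handled. One workable rule is to count the event at the first scan if death or clinical deterioration prevented the second.
4. Make confirmed irPD the point at which mandatory irPFS assessment ends.
5. Reconcile Section 4.4, the non-target subsection and the irPD definition on whether 25% refers to diameters or products.

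The cost is protocol and SAP wording, mostly using scans that are already required. irPFS events become known about 4 weeks later, and some patients with irPD but not RECIST PD may need a confirmatory scan or have to wait for the next scheduled one.
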